1.2 Trial Rationale

1.2.1 Justification for patient population

According to CRUK figures, in 2010 there were 12,180 new cases of NHL with approximately 40-50% being DLBCL and, the vast majority in adults. In the same year, 4,436 died of NHL. For high grade NHL, approximately 60-70% of patients are cured with first line treatment (as shown by recent phase III clinical trials (48). Of those who relapse, approximately 30% would be cured with an intensive chemotherapy approach (approximately 40-50% of those who go through the treatment are cured but a significant proportion of patients are not fit for this approach). This equates to approximately 1100 DLBCL patients with no standard treatment option. Relapsed/refractory DLBCL represents a clear area of unmet need

1.2.2 Justification for design

AZD2014 (vistusertib) is at an ideal stage of development for evaluation in lymphoma patients. It has been subject to a phase I trial which included patients with multiple tumour types (49) and is currently being investigated in several phase II trials in solid tumours. Several dosing schedules have been evaluated and the safety profile is acceptable. If this drug is to benefit patients with haematological

malignancies, rapid phase II studies, alone and in combination with established anti-lymphoma drugs, are required.

Currently in the UK, there are very few studies in the area of relapsed DLBCL and it continues to represent an area of unmet need. The proposed study will therefore provide an additional option for patients with relapsed, refractory DLBCL for which there are no, or few, competing studies, or for patients progressing on or after other clinical studies.

Relapsed DLBCL is relatively uncommon, and patients with this condition are sometimes not well enough to enter a study. Therefore, it is not thought feasible to perform a randomised phase II study. A single arm, A'Herns design utilised in phase II will generate robust evidence of activity for the regimen to be evaluated in an upfront trial.

Assuming that activity and acceptable safety profile is demonstrated for the single agent, we would intend to move on rapidly to investigating combinations. We intend to use the current study as a platform upon which novel combination therapies can be investigated.

The treatment will be considered for further investigation if at least 9 responses are seen from the 30 patients. This results in 90% power to go forward if the underlying response rate is 40%, but only a 13% risk of going forward if the true response rate is 20%

1.2.3 Choice of treatment

New strategies are desperately needed to prolong survival and quality of life. mTOR inhibitors are of proven activity in multiple lymphoma subtypes. In relapsed/refractory DLBCL, the single agent mTOR inhibitor, everolimus, produced an ORR of 30% (50); a further study used the combination of everolimus and rituximab and produced an ORR of 38% with a median duration of remission (DOR) of 8.1 months (51). Although activity was demonstrated in the above studies, ORR was modest and remission was short. A recent but well described, key mechanism of escape from mTORC1 inhibitors is through Akt phosphorylation at Ser 473, which is itself a substrate of the mTORC2 complex (13). Evaluation of dual mTORC1/2 inhibitors has demonstrated markedly reduced Akt phosphorylation (52) which may increase the activity of these agents. There is no clinical data on the efficacy of dual mTORC1/2 inhibitors in DLBCL. The proposed study is therefore designed to evaluate a new class of therapeutic agent which could represent a significant advance over current mTOR inhibitors.

1.2.3.1 AZD2014

AZD2014 is an inhibitor of the kinase activity of mTOR. mTOR is a serine/threonine kinase belonging to the PI3K (PIKK) superfamily of kinases. AZD2014 is specific for mTOR and does not inhibit other members of the PI3K superfamily. The PI3K-Akt-mTOR pathway functions as a sensor of mitogen, energy and nutrient levels and is a central controller of cell growth. The mTOR is a protein kinase (PK) and a vital component of the PI3K/Akt/mTOR signalling pathway. This pathway is deregulated in 50% of all human cancers and, as such, is an important target for inhibitors that would alleviate the unregulated proliferation of cancer cells (53).

Rapamycin and its analogues (rapalogs) are potent inhibitors of mTORC1 and have been shown to be clinically effective in certain cancer types like endometrial cancer, mantle cell lymphoma, renal cell carcinoma and breast cancer (54)(55)(56).

Nevertheless, so far, several resistance mechanisms have been shown to limit the response rate in clinical studies to rapamycin and analogues. mTOR exists as two complexes, mTORC1 and mTORC2, defined by their associated proteins, and having different cellular functions. Rapalogs, due to their allosteric mode of interaction with mTOR, inhibit mainly mTORC1, leaving mTORC2 unregulated. There is also evidence that inhibition of only mTORC1 sets off a negative feedback mechanism that leads to increased Akt signalling.

AZD2014 is selective inhibitor of mTOR kinases and inhibits signalling of both mTOR complexes, mTORC1 and mTORC2. AZD2014 is thereby molecularly different from rapalogs:

- AZD2014 achieves more profound mTORC1 inhibition, in particular inhibiting phosphorylation of the rapamycin insensitive site on 4E-BP1 (T37/46). AZD2014 also inhibits mTORC2.
- AZD2014 has a broader range of growth inhibitory activity *in vitro* across tumour types compared to rapalogs. As such, ATP-competitive dual TORC1/TORC2 inhibitors, like AZD2014 that inhibit both mTOR complexes may offer therapeutic advantages to rapalogs (56).

1.2.3.2 Overall Safety of AZD2014

AZD2014 is considered to be generally well tolerated with most of the AEs classified as CTCAE grade 1 and 2. AEs have also been shown to resolve quickly after short periods of dose interruptions, which allowed patients to stay on the drug for long periods of time (over 1 year). Fatigue, mucositis, rash, nausea, vomiting, diarrhoea, hyperglycaemia and decreased appetite, risk of pneumonitis and infections were the AEs consistently amongst the most frequently reported overall, and those reported as related to AZD2014 by the Investigators. These AEs were also those reported with the highest severity grade and were those AEs most commonly leading to dose interruption and/or permanent discontinuation of AZD2014. These events were generally reversible within 1 week by cessation of AZD2014. The AE profile of continuous and intermittent dosing schedules varied slightly. Although gastrointestinal events were observed more frequently in the intermittent schedules, there have been no reports of rash or hyperglycaemia so far for the intermittent dosing schedules.

Overall, no clinically significant changes were observed in heart rate or blood pressure (BP). Single intermittent systolic or diastolic BP values above and below normal values were reported in a few patients. Intermittent higher heart rates >100 bpm were observed, and tachycardia in some patients.

No clinically significant changes were observed in vital signs or laboratory data overall. Review of emerging laboratory data did not reveal clinically significant liver function test (LFT) abnormalities considered related to AZD2014. Transaminase increases (ALT or AST) were reported as AEs in some patients; the majority were CTCAE grade 1 and were not considered related to AZD2014 by the reporting investigator. Laboratory data suggest that for most patients who do have reductions in cell counts, values return to patients' baseline on stopping AZD2014. The clinical relevance of these changes appears low given that there was no excess of related AEs such as infection, fungal disease, viral disease, dyspnoea, or bleeding within these patients when compared with patients not noted as having reductions, and there were no events of greater severity. ECG repolarisation changes were seen in some patients. However, there were no associated significant QRS morphology changes and the clinical significance of these changes is unknown.

For further information please refer to the current AZD2014 Investigator Brochure (IB).

1.2.3.3 Rituximab

Rituximab is very commonly used and efficacious in DLBCL (57). We plan to add rituximab at standard doses to AZD2014 in a small cohort of 6 patients, to evaluate the safety of this combination. The mechanism of action of rituximab is more complex than first assumed. In addition to the induction of apoptosis (58), complement-dependent (59) and anti-CD20 antibody-dependent cellular cytotoxicity (60), rituximab has been shown to inhibit the phosphorylation of Raf-1, ERK1/2 and MEK1/2 via the upregulation of Raf-1 kinase inhibitory protein (RKIP) (61). This pre-clinical data, together with clinical evidence of efficacy, provides a sound rationale to use this combination in DLBCL (14,51). It is therefore very possible that the addition of Rituximab to the dual mTORC1/2 inhibitor will provide further blockade of the mTOR downstream signalling and therefore potentially enhance the activity of single agent AZD2014.

2. AIMS, OBJECTIVES AND OUTCOME MEASURES

2.1 Aims and Objectives

Assuming that activity and acceptable safety profile is demonstrated for the single agent, we would intend to move on rapidly to investigating combinations. We intend to use the current study as a

platform upon which novel combination therapies can be investigated. The intention is for combination partners to be rationally incorporated, at least in part guided by the results from the proposed biomarker studies.

2.2 Outcome Measures

Primary Outcome Measures

• Best overall response rate (PR plus CR) (using the Revised Response Criteria for Malignant Lymphoma (1), Appendix1) during the first 6 cycles

Secondary Outcome Measures

- Tolerability rate (based on toxicity assessments using CTCAE v 4.0 criteria) of single agent AZD2014
- Tolerability rate of additional toxicities when rituximab is combined with AZD2014 at it's standard dose (stage 2 only)
- Best overall response rate post 6 cycles until the end of the trial, assessed using Revised Response Criteria
- Overall survival (OS) at 1 year
- Progression free survival (PFS) at 1 year
- Duration of response
- Maximum % decrease in the radiological sum of the product of the diameters (SPD) from baseline by CT NCAP

Exploratory Outcome Measures

- Correlation of response with pharmacodynamic biomarkers, cell of origin studies, lymphoidrelated mutational analysis and potential predictive biomarkers of response
- To define the response to AZD2014 by PET CT criteria and analyse the effect of dual mTOR inhibition on PET signal / response when compared to standard CT response

Pre and post treatment biopsies (at subsequent relapse) will be performed to measure relative activity of the mTOR pathway in a biomarker exploratory analysis. Post treatment biopsies will be requested in patients within the rituximab stage to assess for evidence of synergy.

3. TRIAL DESIGN

This is a prospective, single arm, multicentre, phase II clinical trial utilising a two stage design. Stage one will assess the safety and activity of AZD2014 as a single agent in the treatment of DLBCL in 30 patients. Stage two will assess the additional toxicity of combining AZD2014 with Rituximab in an additional 6 patients.

Stage two will be recruited following the full recruitment of stage 1. Stage 2 recruitment will be staggered with 3 patients recruited and their safety data evaluated prior to the recruitment of the remaining 3 patients.

Post treatment biopsies will be requested at relapse in patients receiving rituximab to assess for evidence of synergy.

It is anticipated that the 36 patients required will be recruited over 18 months from specialist centres including the 13 TAP centres.

Once registered to the study, patients will receive AZD2014 125mg bd on an intermittent schedule of 2 days of treatment followed by 5 days with no treatment. Treatment would be on days 1, 2, 8, 9, 15, 16, 22 and 23 of each course 28 days in duration. Treatment is ongoing until progression or withdrawal due to toxicity or patient's choice. For the second stage of the trial, rituximab 375mg/m² will also be administered intravenously on day 1 of the 28 day cycle for a total of 6 cycles in combination with AZD2014.

All patients will be followed for a minimum of 1 year up until disease progression or death.

For patients still on AZD2014 treatment after 1 year (no progression) treatment should still be reviewed at least 3 monthly. Safety, progression and survival data will be collected every 3 months. Assessments should be as per local practice with a CT scan conducted every 3/4 months.

At progression, patients will then be followed up annually for survival data.

Molecular and free DNA sub-study

Tissue, saliva and blood samples will be collected during treatment to determine the activity of AZD2014 on downstream targets, and correlating with response. This will include biopsy tissue from the pre-treatment sample, any biopsy performed on treatment and at relapse post-AZD2014 should this occur.

We are also planning to analyse for predictive biomarkers such as DLBCL cell of origin, non-GCB subtype, lymphoma-associated mutations and for markers of mTORC1 expression. It will be important to see whether high levels of mTORC2 expression (using surrogate markers such as pAKT) and high levels of mTORC1 activity correlate with response to subsequent AZD2014. In addition we will look for markers of resistance; particularly focusing on expression of the MNK1/2 pathway, its effect on phosphorylation of eIF4E and any effect of rituximab on the activity of this pathway.

There is new data to suggest that levels of soluble circulating DNA from tumour cells can predict ongoing response to treatment in patients with DLBCL (62) Recent data has shown that levels of immunoglobulin gene measurements specific to the tumour type (tumour-specific clonotypes) measured by PCR can predict relapse following treatment in the first line setting in DLBCL. As part of an optional sub-study we are interested in monitoring soluble tumour DNA by PCR from the peripheral blood and saliva at screening and in peripheral blood only after 2 cycles, after 6 cycles, and at progression. Additional samples will be taken in responding patient every 3 months for up to a year. These samples will be collected and stored for future investigations as to whether free DNA correlates with treatment response in the relapsed setting.

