12.6 Power Calculations

The sample size calculation is based on A'Hern's single stage phase II design. A total of 30 patients will be recruited in the main section of the study.

Activity

The treatment will be considered for further investigation if at least 9 responses are seen from the 30 patients. This results in 90% power to go forward if the underlying response rate is 40%, but only a 13% risk of going forward if the true response rate is 20% or less.

Toxicity

A Simon 2 stage design is proposed, using tolerability (i.e. opposite of toxicity) as the outcome.

A tolerability rate of 60% would not be acceptable, a tolerability rate of 80% would be.

The study would need to observe at least 10 'tolerable' outcomes (i.e. at most 5 toxicities that lead to treatment delays or dose modifications during the first 2 cycles) from the first 15 patients, and at least 21 'tolerable' outcomes (i.e. .at most 9 toxicities that lead to treatment delays or dose modifications

during the first 2 cycles) from the overall 30 to conclude that the treatment was tolerable at the current dose. This gives 90.4% power to conclude that treatment is tolerable when it is, but a 15.3% risk of concluding that the treatment is tolerable, when in fact it is not. If the treatment is too toxic then there is a 59.7% chance of stopping the trial at the halfway point.

For the combination stage at least 2 tolerable outcomes (i.e. at most 1 toxicity that leads to a treatment delay or dose modifications) during the first 2 cycles from the first 3 patients would need to be observed to continue recruitment. 4 tolerable outcomes (i.e. at most 2 toxicities that lead to treatment delays or dose modifications) are required during the first 2 cycles for the overall 6 to conclude that the combination treatment was tolerable at the current dose.

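### Stage 2 opens on full recruitment of stage 1, about 8 to 9 weeks before the 21-of-30 tolerability count can be complete, and nothing ties its opening to that count

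*Protocol*

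**What the plan says.** - **Trigger for stage 2.** Section 3: "Stage two will be recruited following the full recruitment of stage 1". This is an enrolment milestone and carries no outcome condition.
- **Dose in stage 2.** Sections 3 and 7.2 keep the stage 1 AZD2014 dose and schedule and add rituximab: "rituximab 375mg/m² will also be administered intravenously on day 1 of the 28 day cycle for a total of 6 cycles in combination with AZD2014".
- **Tolerability rule.** Section 12.6: "A tolerability rate of 60% would not be acceptable, a tolerability rate of 80% would be". For the first 15 patients, "The study would need to observe at least 10 'tolerable' outcomes". For all 30, it requires "at least 21 'tolerable' outcomes", each judged over the first 2 cycles, "from the overall 30 to conclude that the treatment was tolerable at the current dose".
- **Planned looks.** Section 12.4 lists two: after 15 patients, expressly as guidance, and after the first 3 combination patients. Neither is the 30-patient count.
- **Stage 2 stagger.** Sections 3 and 12.6 recruit 3 patients and require at least 2 tolerable outcomes over 2 cycles before the other 3 enter. The overall requirement is then 4 of 6.
- **Oversight.** Section 13.4 gives the Trial Safety Committee the final say on continuation. Its scheduled meetings are at 6 months or after 15 patients have completed 6 cycles, and yearly after that.

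**The concern.** Stage 2 is there to measure what toxicity rituximab adds to AZD2014 at a given dose. The trial has a rule for deciding whether that dose is tolerable alone, but stage 2 can open before the rule can be applied. The protocol is also silent on what happens to stage 2 if the rule is not met.

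Two things are at stake. Some patients could receive the two-drug regimen at a dose that the trial's own criterion then finds not tolerable. And a favourable 4-of-6 result would be hard to interpret as added toxicity if the single-agent base had missed its criterion.

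**Working it through.** **Inputs**
- Tolerability rates: 60% unacceptable, 80% acceptable (section 12.6).
- Rules: at least 10 of 15, then at least 21 of 30 (section 12.6).
- Cycle length 28 days (section 7.2); treatment starts within 7 days of registration (section 6).
- Accrual: 36 patients in 18 months (section 3), i.e. 2 per month. Uniform accrual is an assumption.

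**1. Reproducing the plan's figures.** Let X1 and X2 be independent Bin(15, p), the tolerable outcomes in the first and second 15 patients.
- P(stop at 15) = P(X1 ≤ 9)
- P(meet both) = sum over x = 10 to 15 of P(X1 = x) × P(X2 ≥ 21 − x)

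Terms at p = 0.60:

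| x | P(X1 = x) | P(X2 ≥ 21 − x) | Product |
|---|---|---|---|
| 10 | 0.1859 | 0.2173 | 0.0404 |
| 11 | 0.1268 | 0.4032 | 0.0511 |
| 12 | 0.0634 | 0.6098 | 0.0387 |
| 13 | 0.0219 | 0.7869 | 0.0173 |
| 14 | 0.0047 | 0.9050 | 0.0043 |
| 15 | 0.0005 | 0.9662 | 0.0005 |

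With unrounded terms, P(X1 ≥ 10) = 0.4032 and P(meet both) = 0.1521. Early stopping at 60% is therefore 59.7%, as stated. The risk of accepting at 60% is 15.2% (stated 15.3%; the difference is immaterial here). Power at 80% is 90.5% (stated 90.4%).

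**2. Chance that stage 2 opens and the dose then misses 21 of 30.** This is P(X1 ≥ 10) − P(meet both), taking the 10-of-15 rule as followed.

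| True tolerability | Meets 10/15 | Meets both | Opens, then misses 21/30 |
|---|---|---|---|
| 60% | 40.3% | 15.2% | 25.1% |
| 70% | 72.2% | 53.4% | 18.8% |
| 80% | 93.9% | 90.5% | 3.4% |

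**3. When the count is complete.** Two cycles are 2 × 28 = 56 days. With up to 7 days to first dose, the count closes 56 to 63 days after the 30th registration, i.e. 8 to 9 weeks. At 2 patients per month, 2 × 56 / 30.44 = 3.7 to 2 × 63 / 30.44 = 4.1 stage 1 patients are still in their window at full recruitment.

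**4. What is known at full recruitment.** With 4 patients pending and p = 0.60, a miss is already certain (at most 16 tolerable of 26) in 12.5% of trials. The count is still open in 25.7%, of which 12.6 points end in a miss. The two routes sum to 12.5% + 12.6% = 25.1%, as in step 2. At p = 0.80 the corresponding figures are 0.8%, 35.4% and 2.6%.

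**5. Combination patients exposed before the count closes.** If stage 2 follows directly at 2 per month, its third patient registers about 1.5 months (some 6 weeks) after the 30th. That patient's 2 cycles take a further 8 weeks, so patients 4 to 6 enter at about 14 weeks, after the count has closed at 8 to 9 weeks. About three patients are exposed by then.

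**6. The 2-of-3 look as a backstop.** At 60% tolerability with no added rituximab toxicity it is passed with probability 3 × 0.6² × 0.4 + 0.6³ = 0.648. It acts only after those three patients have been dosed.

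**The case against.** **Six patients, or a finished stage 2.** A reader might infer that all six combination patients could be treated before the dose misses its criterion. The stagger rules this out: the 2-of-3 look needs 2 cycles from three patients recruited after stage 1 is full. Its window ends no earlier than that of the 30th stage 1 patient, apart from the 7-day start allowance.

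**A contradiction with sections 1.2.2 and 2.1.** Section 2.1 says "Assuming that activity and acceptable safety profile is demonstrated for the single agent, we would intend to move on rapidly to investigating combinations", and a reader might take this as a gate that section 3 breaks. Both sections go on to describe the study as a platform for new combinations, and section 2.1 wants partners guided partly by the biomarker results. Rituximab is already fixed as the stage 2 partner, so the sentence can be read as concerning later combinations. It also requires activity, which a tolerability gate alone would not satisfy. The point does not rest on it.

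**The committee can act.** Section 13.4 gives it confidential analyses, authority over continuation and extra or emergency meetings, and section 8.2.5 has it review all serious adverse events. The trigger in section 3 sets an order and does not compel immediate opening. This stands as a partial safeguard. In about half of the 25.1% at 60% tolerability, the miss would already be visible at full recruitment and the committee could act on it. But no meeting is tied to the 30-patient count, and no text says that a count below 21 bears on stage 2.

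**Missing 21 of 30 is not proof of harm.** An intolerable outcome is any toxicity leading to a treatment delay or dose modification. Under section 7.5.2.2 that can include a hold for Grade 2 stomatitis, resumed without a reduction. A miss means only that the protocol's own criterion for tolerability at the current dose is not met.

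**Conclusion.** The point holds as a gap in sequencing. Followed as written, the protocol can open the combination before its single-agent tolerability criterion can be assessed, and it says nothing about the consequence of a miss. The chance of opening and then missing is 25.1% at a true tolerability of 60%, 18.8% at 70% and 3.4% at 80%. It is therefore a material risk if the dose is poorly tolerated and a small one if it is well tolerated.

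The figures assume independent outcomes, a common tolerability rate and adherence to the 10-of-15 rule, which section 12.4 calls guidance. If that rule were ignored altogether, the 60% figure could reach 1 − 0.176 = 82.4%, where 17.6% is the chance of at least 21 of 30 with no interim look. The estimate of about three exposed patients also assumes uniform accrual of 2 per month.

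A reader might take the 25.7% still undecided at full recruitment as the risk. It is not: only 12.6 points of it end in a miss.

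**What to change.** Reconcile sections 3, 12.4 and 12.6. State in sections 3 and 12.4 that stage 2 opens only after all stage 1 patients have completed 2 cycles or left treatment and the Trial Safety Committee has reviewed the count against the protocol's own 21-of-30 criterion. If the count is below 21, the committee records its decision and its reasons. An absolute bar with a compulsory amendment would go further than the pragmatic approach that section 12.4 takes to stopping, and is not needed to close the gap.

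**Cost.** A pause of about 8 to 9 weeks between the 30th stage 1 registration and the first stage 2 registration, plus time for data return and convening the committee. If the criterion is applied strictly, the chance of opening stage 2 at 80% true tolerability falls from 93.9% to 90.5%; at 60% it falls from 40.3% to 15.2%. No extra patients or procedures are required.
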